#### 4.2 Patient Disposition and Data Sets Analyzed

The number of subjects included in each of the ITT, PP and safety populations will be summarized for each treatment group and overall. The number and percentage of subjects randomized and treated will be presented. Subjects who completed the study and subjects who withdrew from study prematurely will also be presented with a breakdown of the reasons for withdrawal by treatment group for the ITT, PP and safety populations.

#### 4.3 Protocol Violations/Deviations

Major protocol deviations are those that are considered to have an effect on the analysis. A list of potential major protocol deviations will be generated programmatically from the data captured before the clean file meeting. The clinical monitor of the study will review the list and the finalisation of the major protocol deviations will be done at the clean file meeting.

The number of subjects with major protocol deviations will be summarized per treatment group.

#### 4.4 Demographics and Baseline Characteristics

Demographics and baseline characteristics will be summarized by treatment group for the ITT and PP populations and analyzed according to the methods described in section "General Methodology" above.

#### 4.5 Medical History

Medical and surgical history will be summarized by system organ class (SOC) and preferred term (PT) for each treatment group for ITT population.

STATISTISKA KONSULTGRUPPEN		Statistical Analysis Plan	
Protocol: A randomized, double blind, parallel study to evaluate the performance and safety of the Zolidd One ExHex dental implant in subjects with partial edentulism		Protocol No: ADD-001	Version: 1.0 Page 12 of 18

#### 4.6 Surgical Variables

Implants position will be summarized for each treatment group for ITT population.

#### 4.7 Prior and Concomitant Medications and Other Dental Procedures

Prior and concomitant medication will be summarized by higher level anatomical therapeutic classification (ATC) group and generic term for each treatment group for ITT population.

#### 4.8 Efficacy Analyses

##### 4.8.1 Primary Efficacy Analysis

Primary efficacy analysis will be the comparison of change in ISQ highest value for coated implant with change in ISQ highest value for the uncoated implant on the “index implant” from day 1 to 12 weeks visit with Fisher’s non-parametric permutation test on the ITT-population at significance level 0.05. For primary efficacy variable the 95% confidence interval for the mean difference between the coated and the uncoated implants is obtained by inversion of Fisher’s non-parametric permutation test by means of simulation.

If the 12 weeks ISQ highest values are missing Last observation carry forward (LOCF) will be used from 8 weeks, if available. For the cases of implant loss ISQ = 0 at 12 weeks will be imputed in the main analysis, i.e. resulting in negative difference in ISQ for the subject. For the cases where week 8 and week 12 values are not available due to other reasons than implant loss, same value as baseline value will be imputed, i.e. the difference of 0 will be imputed.

Primary efficacy analysis will be presented per centre and a separate analysis will also be performed in order to study centre effect for primary variable. In case of few centres, centre will be analyzed as fixed effect.

If significant differences are found between the two randomised groups in important baseline predictors a complementary primary efficacy analyses will be performed adjusted for these variables using analysis of covariance (ANCOVA).

Following sensitivity analyses will be performed for the primary efficacy variable:

- Multiple imputations: using analysis of variance for the unadjusted analysis and analyses of covariance for the adjusted analysis if needed. When using multiple imputations LOCF should not be applied. For the sensitivity analysis missing values due to lost implants will be handled with multiple imputation. Following rules will be applied:
  - The multiple imputation will be performed separately for the two study treatment groups to avoid cross-contamination of imputation models between the groups, using PROC MI procedure in SAS version 9.4 and fully conditional specification (FCS) with regression method (REG), per treatment group.
  - The following seed will be used for both groups: 545399
  - The outcome variable of change in ISQ from day 1 will be imputed
  - All baseline characteristics, baseline ISQ value and any follow-up ISQ will be included if they are associated with at least  $r \geq 0.40$  to the difference in ISQ at 12 weeks or the actual ISQ value at 12 weeks, or if the variables are

STATISTISKA KONSULTGRUPPEN		Statistical Analysis Plan	
Protocol: A randomized, double blind, parallel study to evaluate the performance and safety of the Zolidd One ExHex dental implant in subjects with partial edentulism		Protocol No: ADD-001	Version: 1.0 Page 13 of 18

associated with the missingness of the difference in ISQ at of at least 0.10 significance level.

- 50 study samples will be imputed and pooled by using PROC MIANALYZE procedure
- Trace plots of means and standard deviations of imputed variables will be reviewed checking that the multiple imputation has worked properly
- Worst case scenario analysis: using the same imputation rules as specified above for the coated implant group, but imputing the difference in ISQ equal to 0, i.e. impute baseline value for week 12 visit, for uncoated implant group no matter the reason for missing data (also for implant loss).

Complementary analyses between the two randomized groups of the primary efficacy variable will be done on the PP-population.

The results from the analyses of primary variable will be given both in tables and figures.

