9.2 Anticipated adverse device effects

The most common early post-surgical symptoms in dental implant surgery are swelling, pain, numbness of nerve and/or infection.

Further problems in common include problems associated with failure of the integration or fracture of the implant and/or subsequent loosening, causing revision surgery. These problems may occur but are expected to be of low frequency since the investigational devices used in this study are designed as a generic model of the established Nobel Biocare Bränemark implant with low frequency of such problems.

Known risk factors for long term success are insufficient bone volume, infection, inadequate soft tissue, uncontrolled diabetes, smoking, bruxism, unfavourable jaw relationships, or-facial radiotherapy, and steroid therapy, systemic treatment with bisphosphonates or chemotherapy. The same general precautions apply in this clinical investigation as with any dental implant surgery.

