### **1.4 Sample Size**

The power analysis based on Abtahi et al. 2012: The SD for change in ISQ value from placement to month 6 was 5.3 in the active group and 5.4 in the control group. In order to be able to find a clinical difference of five ISQ highest values in change between placement and 12 weeks between the coated and the uncoated group with Fisher's non-parametric permutation test with 90% power 28 evaluable subjects are needed in each group assuming a SD for change in ISQ in each group of 5.6 and a significance level 0.05. Thirty-one subjects will be randomized to each study group to compensate for 10% drop-out. A total of 62 subjects will be randomized to the two groups.

STATISTISKA KONSULTGRUPPEN		Statistical Analysis Plan	
Protocol: A randomized, double blind, parallel study to evaluate the performance and safety of the Zolidd One ExHex dental implant in subjects with partial edentulism		Protocol No: ADD-001	Version: 1.0 Page 7 of 18

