### 3.2.2 *Secondary Efficacy Variables for Part I*

- Absolute ISQ highest value at day 1, week 8 and week 12 after implantation for “index implant”
- Incidence of post-surgery complications and adverse events up to week 12 post-implantation visit
- Change in ISQ highest value from day 1 to 8 weeks for the “index implant”
- Change in ISQ highest value from day 1 to week 8 and 12 for all other implants
- Absolute ISQ highest value at day 1, week 8 and 12 for all other implants
- Survival rate up to 12 weeks for all implants.

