#### 3.3.2 Implant Status and Soft Tissue Status

Implant status and Soft tissue status are measured at each visit.

Implant status is coded as: OK / Questionable / Loose.

Soft tissue status is coded: Neither red or swollen / Red / Swollen / Red and swollen

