### 6 CHANGES OF ANALYSIS FROM PROTOCOL

This statistical analysis plan has been written and finalised prior to database lock and revealing of randomized treatment groups. Following changes to protocol were made:

- Added survival rate up to 12 weeks for all implants in Part I analysis/report.
- Marginal bone height will only be analyzed in Part II analysis/report for all study visits.
- ITT population has been changed from 'all randomized subjects with at least one performance measurement after implantation' to 'randomized subjects with at least one study implant' including few specific cases as described in section 2.1.1.
- The imputation of missing data has been updated to also handle implant loss cases.

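### SAP 1.4 keeps the 90% power figure although SAP 4.8.1 now scores a lost index implant as ISQ 0; unless losses are very rare or fall mainly in the uncoated arm, the planned primary test has less power

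*SAP*

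**What the plan says.** SAP 1.4 repeats Protocol 18.8: to detect a difference of 5 ISQ units in change from placement to week 12, "90% power 28 evaluable subjects are needed in each group assuming a SD for change in ISQ in each group of 5.6", with 31 randomised per group to cover 10% drop-out. The SD sits just above the 5.3 and 5.4 reported for the earlier trial that it cites.

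SAP 4.8.1 keeps the protocol's primary test, Fisher's permutation test on change in the highest ISQ, with a confidence interval for the mean difference. It then sets three imputation rules:

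- Week 12 missing: "Last observation carry forward (LOCF) will be used from 8 weeks, if available".
- Implant lost: "For the cases of implant loss ISQ = 0 at 12 weeks will be imputed in the main analysis".
- Weeks 8 and 12 both missing for another reason: a change of 0.

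SAP 6 declares the addition: "The imputation of missing data has been updated to also handle implant loss cases". Nothing there or in SAP 1.4 revisits the SD or the power.

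On how often loss might occur, Protocol 9.2 says of failed integration, fracture and loosening only that "These problems may occur but are expected to be of low frequency". No day-1 ISQ level is given.

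**The concern.** The test statistic is a difference in means. An index implant lost from a day-1 ISQ of 60 contributes a change of −60, more than ten SDs (60/5.6 = 10.7) from the rest of the data. An SD of 5.6 cannot already contain such values: one change of −60 among 28 otherwise identical values gives a sample SD of 60/√28 = 11.3.

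So the outcome distribution changed and the power statement did not. A reader of SAP 1.4 would take 90% as the power of the analysis now planned. The trial could miss a true 5-point benefit because of one or two losses, and nobody would have been told in advance how likely that was.

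**Working it through.** **The plan's own figure.** Two-sided 0.05, difference 5, SD 5.6, noncentral t: power is 89.6% at 27 per arm, 90.7% at 28 and 93.3% at 31. The stated 28 reproduces. A simulated permutation test without losses gives about 91% at 28 and 93–94% at 31.

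**Inputs.** From the documents: difference 5, SD 5.6 among retained implants, 31 per arm, two-sided 0.05, ISQ = 0 for a loss. Assumed: loss rate p, mean day-1 ISQ m (40 to 80) with SD 7, normal changes, uncoated mean change 0, and lost implants kept in the ITT set (SAP 2.1.1 is not visible).

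**Mean and SD under the rule.** With retained mean d (5 coated, 0 uncoated), an arm's mean is (1−p)d − pm. With equal p the expected difference is 5(1−p), which is 4.95 at 1%. The variance is (1−p)(5.6² + d²) + p(7² + m²) − ((1−p)d − pm)². At p = 1%, m = 70:

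- coated: 0.99 × 56.36 + 0.01 × 4949 − 4.25² = 55.8 + 49.5 − 18.1 = 87.2
- uncoated: 0.99 × 31.36 + 49.5 − 0.7² = 31.0 + 49.5 − 0.5 = 80.0

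The averaged variance is 83.6, an SD of 9.1 against 5.6. The treatment effect hardly moves; the noise grows. Putting this SD into a t-test formula is too pessimistic, because most trials at this rate have no coated loss, so the planned test was simulated.

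**Average power, equal loss in both arms, no drop-out** (999 permutations, 4,000–6,000 trials per setting for rates from 0.25% up; repeat runs agree within about 3 points):

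| Loss per arm | Day-1 ISQ assumed | Power |
|---|---|---|
| 0.1% | 70 | about 91–92% |
| 0.25% | 60–80 | 87–88% |
| 0.5% | 40–80 | 80–85% |
| 1% | 40–80 | 69–79% |
| 2% | 40–80 | 53–66% |

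**Where the power goes.** With exactly one coated loss, power is 39, 25, 12, 5 and 2% at day-1 ISQ 40, 50, 60, 70 and 80. With one uncoated loss only, it is 96–97% (ISQ 60–80). The chance of at least one coated loss is 1 − (1−p)³¹: 14% at p = 0.5%, 27% at 1%, 47% at 2%. As a cross-check at 1% and ISQ 70, taking about 94% power without a coated loss and about 5% with one: 0.73 × 94% + 0.27 × 5% ≈ 70%.

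**Unequal loss** (coated vs uncoated, ISQ 60–80): 0% vs 2% gives 95%; 0.5% vs 1.5%, 81–83%; 1% vs 3%, 72–75%; 2% vs 1%, 51–55%.

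**Type I error** at 1% equal loss: 5.1–5.7%, nominal within simulation error.

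**Drop-out scored as 0.** If all of the planned 10% drop-outs had neither follow-up value, power would be about 86–90% with no implant lost, and about 63–69% at 1% loss and ISQ 70 (uncoated mean change from −5 to +5). This bounds the effect: some drop-outs would have a week-8 value, and Protocol 18.10 expects under 5%.

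**Ranks of change, losses lowest.** Power is 91–92% with no loss, 91–92% at 0.5–1% loss, 89–90% at 2%, and 86% after exactly one coated loss. At ISQ 70 with one coated loss, the planned interval averages −2.5 to 7.4, and a Hodges-Lehmann interval 1.7 to 7.7.

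**The case against.** The strongest reply is that the size rests on two inputs the documents do not supply, and on equal loss, when the premise of the trial is better integration with the coating. That stands: no row of the table is a property of the plan. Protocol 9.4 also allows a loosened implant to stay in place, and SAP 3.3.2 says "Implant status is coded as: OK / Questionable / Loose", so not every integration failure need be scored as lost. The rate that matters is the rate scored 0.

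Scoring loss as failure is a declared and defensible choice, and it keeps the type I error. That also stands; the point concerns the power statement.

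It can be said that sensitivity analyses already exist. They help interpretation, but none counts loss as the worst outcome without the extreme value. Multiple imputation replaces a loss with a predicted change, as if the implant had survived. The worst-case analysis, "using the same imputation rules as specified above for the coated implant group", keeps the zero for coated losses and gives uncoated losses a change of 0. The secondary variable "Survival rate up to 12 weeks for all implants" counts losses over all implants, separately from the ISQ comparison.

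A reader might infer that the 90% fails as soon as any coated loss is possible. It does not: at 0.1% loss average power is still above 90%. The very low figures after one coated loss are conditional on that loss. Nor does the 90% hold whenever no implant is lost, because drop-outs scored as 0 can lower it too.

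A reader might also see a conflict between the loss rule and LOCF for an implant lost after week 8. SAP 4.8.1 gives loss its own rule, and that is the natural reading; a clause on this would only clarify.

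**Conclusion.** The concern holds as a gap in the power statement. SAP 1.4 describes a comparison of observed changes with SD 5.6. The main analysis in SAP 4.8.1 includes zeros for lost implants, and its power falls below 90% unless losses are very rare or fall mainly in the uncoated arm. The size depends on assumption: 80–85% at 0.5% equal loss, 69–79% at 1% and 53–66% at 2%, for day-1 ISQ 40–80, with 31 per arm, no drop-out, and lost implants kept in the ITT set.

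A reader might go further and conclude that the primary test is invalid, that the treatment effect is diluted, or that the trial is underpowered as a fact. The documents support none of these. Type I error is preserved, the expected difference is nearly unchanged, and the true loss rate is unknown. It should be fixed before unblinding; confidence is medium because the loss rate and day-1 ISQ are assumed.

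**What to change.** Before unblinding:

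1. In SAP 1.4, state that the 90% is the design calculation for 28 evaluable subjects per arm with observed changes, and that it predates the SAP 4.8.1 imputation rules. Give the power of the planned primary analysis over a stated range of loss rates (equal and unequal), day-1 ISQ, and drop-out scored as 0. Do not say that 90% holds whenever no implant is lost.
2. In SAP 4.8.1, add a sensitivity analysis that permutes the ranks of change with lost index implants ranked lowest. Report it with a Hodges-Lehmann shift, its 95% confidence interval, and the number of index-implant losses per arm. This does not restore the power of the primary test. It shows whether a few zeros drive the result while still treating loss as the worst outcome.

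Optional: a clause that the loss rule overrides LOCF when an implant is lost after week 8.

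The cost is a short SAP revision. No new data are needed, and the primary test and effect measure stay as they are.

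Making the rank test primary is a separate choice for the sponsor and not part of this fix. It would cost about 1–2 points of power if no implant is lost, replace the mean difference with a location shift, and give a single loss less weight. It would have to be declared in SAP 6 as Protocol 18.12 requires, and handled under Protocol 20.

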18.2 General methodology

The design of the study is a two parallel group design. The main efficacy analyses will be performed on the Intention-to-Treat (ITT) populations between the two groups. Complementary performance analyses will be performed on the Per Protocol (PP) population. See section 18.4 below.

For comparison between the two randomized groups regarding “index implant”, Fisher’s non-parametric permutation test will be used for continuous variables, Mantel-Haenszel chi-square test for ordered categorical variables, and Chi-square test for non-ordered categorical variables and Fisher’s exact test for dichotomous variables.

For primary efficacy variables and for other important continuous efficacy variables the 95% confidence interval for the mean difference between the two groups will be obtained by inversion of Fisher’s non-parametric permutation test by means of simulation.

For comparison between the two randomized groups regarding analysis of all teeth within subjects a mixed model with random effects analysis adjusting for within subject correlation will be used.

If significant clinical relevant differences are found between the two randomised groups in important baseline variables, then complementary efficacy analyses will be performed adjusted for these variables.

For comparison over time within randomized groups Fisher’s non-parametric permutation test for paired observations will be used for change in continuous and Sign test for change in ordered categorical variables or change in dichotomous variables.

The distribution of the variables will be given as mean, SD, median, minimum and maximum for continuous variables and as number and percentages for categorical variables.

Time to loss of implant will be described with Kaplan-Meier curves and analysed with Log-rank test between the two randomised groups.

All significance tests will be two-sided and conducted at the 5% significance level.

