## 4 STATISTICAL METHODOLOGY

### 4.1 General Methodology

The design of the study is a two parallel group design. All main efficacy analyses will be performed on the ITT population. Complementary efficacy analyses will be performed on the PP population.

For comparison between the two groups (coated vs uncoated), when we have only one observation per subject, Fisher's non-parametric permutation test will be used for continuous variables, Fisher's exact test for dichotomous variables, Mantel-Haenszel chi-square test for ordered categorical variables and Chi-square test for unordered categorical variables.

For primary efficacy variables and for other important continuous efficacy variables the mean difference between the two groups with 95% confidence interval (CI) will be given. For dichotomous variables the percentage in each group together with the difference in percentage between the two groups with 95% confidence interval will be calculated with Miettinen and Nurminen's method.

If clinically relevant significant differences are found between the two randomised groups in important baseline predictors a complementary primary efficacy analyses will be performed

STATISTISKA KONSULTGRUPPEN		Statistical Analysis Plan	
Protocol: A randomized, double blind, parallel study to evaluate the performance and safety of the Zolidd One ExHex dental implant in subjects with partial edentulism		Protocol No: ADD-001	Version: 1.0 Page 11 of 18

adjusted for these variables using analysis of covariance (ANCOVA) for continuous outcome variables and with multivariable logistic regression for dichotomous outcome variables.

For comparison between the two groups (coated vs uncoated), when we have more than one observation for all or for some subjects, a mixed model with random effects will be used for continuous outcome variables and a General Estimating Equation (GEE) model is used for dichotomous outcome variables. In both these models the dependence within observation are taken into account correctly. For non-normal continuous variables the mixed model will include an empirical bias correction with robust standard errors.

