#### 4.8.4 Exploratory Efficacy Analyses

Univariable and multivariable analyses of baseline predictors to primary efficacy variable will be performed using mixed models as specified in *General Methodology* above followed by forward stepwise multivariable model on the ITT population on all implants. The variables to be examined are:

- Age
- Sex
- Bone quality
- Bone quantity
- Implant position
- Smoking
- Alcohol
- Diabetes.

STATISTISKA KONSULTGRUPPEN		Statistical Analysis Plan	
Protocol: A randomized, double blind, parallel study to evaluate the performance and safety of the Zolidd One ExHex dental implant in subjects with partial edentulism		Protocol No: ADD-001	Version: 1.0 Page 14 of 18

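### The primary comparison of change in ISQ is adjusted only after a significant baseline difference, and no planned analysis is certain to adjust for day-1 ISQ

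*SAP*

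**What the plan says.** The primary analysis in SAP 4.8.1, as in Protocol 18.5.1, is Fisher's permutation test on change in the highest ISQ of the index implant from day 1 to week 12. It has no covariate, so day-1 ISQ enters only by subtraction.

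ANCOVA is a complementary analysis that depends on a baseline test: "If significant differences are found between the two randomised groups in important baseline predictors a complementary primary efficacy analyses will be performed adjusted". SAP 4.1 words the condition more narrowly: "If clinically relevant significant differences are found between the two randomised groups in important baseline predictors". Protocol 18.2 also asks for clinical relevance: "If significant clinical relevant differences are found between the two randomised groups in important baseline variables, then complementary efficacy analyses will be performed". None of these places names the predictors.

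The multiple-imputation sensitivity analysis carries the same condition: "analyses of covariance for the adjusted analysis if needed". Its imputation model names day-1 ISQ, but only subject to a screening rule: "All baseline characteristics, baseline ISQ value and any follow-up ISQ will be included if they are associated with at least" a stated correlation, or if they relate to missingness.

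Day-1 ISQ is not in the baseline list of SAP 3.1.1, nor among the eight predictors of SAP 4.8.4 ("Univariable and multivariable analyses of baseline predictors to primary efficacy variable will be performed using mixed models"). The interaction analyses of SAP 4.8.5 have no trigger but do not name it. For centre, "a separate analysis will also be performed in order to study centre effect for primary variable", again without a trigger, though the text does not say that this yields an adjusted treatment estimate. SAP 3.2.2 lists absolute ISQ at day 1, week 8 and week 12 for comparison between groups.

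**The concern.** Under randomisation, a baseline p-value measures only chance. It does not show whether a variable predicts the outcome, which is what makes adjustment worthwhile. The rule therefore fires by chance in 5% of trials for each variable tested, stays silent for imbalances just short of 0.05, and leaves the choice of covariates until the data are seen.

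Day-1 ISQ is the obvious covariate. Analysing change fixes its slope at 1, and analysing absolute week-12 ISQ fixes it at 0. If the true slope lies between, the two planned comparisons bracket the adjusted estimate, but nothing is certain to report it. At stake are some precision and some protection against chance imbalance in the one trial that is run.

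**Working it through.** **Inputs from the documents** (Protocol 18.8, SAP 1.4): difference 5 ISQ, SD of change 5.6, two-sided 0.05, 28 evaluable and 31 randomised per arm.

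**Assumed inputs:** the correlation r between day-1 and week-12 ISQ, and the ratio k of week-12 SD to day-1 SD. Neither is in the documents, so both are varied.

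**The plan's own figure.** A two-sample t calculation needs 27.36, so 28 per arm, with power 90.7% (noncentrality 5 / (5.6 × √(2/28)) = 3.34, 54 df). A simulated permutation test at 28 per arm gives 90.0%. The stated size reproduces.

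**Power with adjustment, no lost implants.** Day-1 SD is s₁ = 5.6 / √(1 + k² − 2rk). The residual SD given day-1 ISQ is k·s₁·√(1 − r²). For k = 1 and r = 0.5, s₁ = 5.6 and the residual SD is 5.6 × √0.75 = 4.85. Power uses 53 df.

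**Shift from an imbalance that does not trigger.** The largest non-significant day-1 difference at 31 per arm is t(0.975, 60) × s₁ × √(2/31), and it moves the change difference by (1 − rk) times that amount. For k = 1 and r = 0.5: 2.00 × 5.6 × 0.254 = 2.85, times 0.5 = 1.42 ISQ. The average over all non-triggering trials replaces 2.00 by the mean of |Z| given |Z| < 1.96, which is 2(0.3989 − 0.0584)/0.95 = 0.717. That gives 0.51 ISQ.

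| r (k = 1) | Day-1 SD | Residual SD | Power, 28 per arm | Largest shift | Mean absolute shift |
|---|---|---|---|---|---|
| 0.3 | 4.73 | 4.51 | 98.2% | 1.68 | 0.60 |
| 0.5 | 5.60 | 4.85 | 96.6% | 1.42 | 0.51 |
| 0.7 | 7.23 | 5.16 | 94.5% | 1.10 | 0.39 |
| 0.9 | 12.52 | 5.46 | 92.0% | 0.64 | 0.23 |

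With k = 0.7, adjusted power exceeds 99% at every r. With k = 1.3 it is 95.5, 93.0, 90.9 and 92.8%, so at r = 0.7 there is no real gain.

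**With lost implants.** The SAP states: "For the cases of implant loss ISQ = 0 at 12 weeks will be imputed in the main analysis". Assume a mean day-1 ISQ of 65, equal loss in both arms and 31 per arm. Simulation compared the unadjusted permutation test with a permutation test on residuals after day-1 ISQ and centre, for k = 0.7, 1 and 1.3:

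- 2% loss: power goes from 53–57% to 55–59%; the change ranges from −0.4 to +2.9 points.
- 5% loss: power goes from 27–30% to 27–29%; the change ranges from −0.8 to +1.1 points.

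The few very large negative changes dominate the variance, and day-1 ISQ does not predict them. The multiple-imputation analysis imputes lost implants instead of scoring them 0, so the no-loss gain is the relevant guide there.

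**The case against.** The strongest reply is that nothing is wrong with the primary analysis. Protocol and SAP agree on endpoint, test and sample size, and the trial has its stated power on its own inputs. The conditional ANCOVA is only complementary, so the trigger cannot change the primary result. All of that stands.

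The reply can add that the large power gain needs a trial with no lost implants. At an assumed 2% loss per index implant, the chance of at least one loss among 62 is 1 − 0.98⁶² = 71%, and under the ISQ = 0 rule little gain is then left in the main analysis. That also stands, and it limits the claim.

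A reader might infer that the unadjusted test has an inflated false-positive rate. Given a day-1 imbalance exactly at the p = 0.05 boundary, the rate is 16, 12, 9 and 6% for r = 0.3, 0.5, 0.7 and 0.9 at equal SDs. But that is the extreme. Over all trials that do not trigger it is 4.0–4.9% (normal approximation), and over all randomisations it is 5%.

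A reader might also infer that ANCOVA must replace the permutation test. The documents do not support that either: the agreed test is valid and powered. Moreover, day-1 ISQ is measured after the allocated implant is seated (Protocol Appendix 2, step 6), so adjusting for it rests on an assumption that deserves to be explicit.

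What the reply does not rescue is the trigger itself, the unnamed predictors, the two wordings of the condition, or the lack of any analysis certain to adjust for day-1 ISQ. Because SAP 3.2.2 compares day-1 ISQ between groups, an imbalance would be seen, but seeing it is not adjusting for it.

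**Conclusion.** The point holds as an improvement to the supporting analyses. Adjustment hangs on a significance test of unnamed predictors, and day-1 ISQ, which is already collected, may never be used as a covariate. It is not an error in the size of the test, not a bias over randomisations, and not a shortfall in the planned sample size.

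Its value depends on how many implants are lost. With none, adjusted power at 28 per arm is 92–98% against 90.7% (equal SDs, r from 0.3 to 0.9). With losses scored 0, the gain is at most about 3 points at 2% loss and about none at 5%. The shift from an undetected imbalance is usually small, 0.2–0.6 ISQ on average and 0.6–1.7 at the boundary, against a target of 5. The correlation, the SD ratio, the loss rates and the mean day-1 ISQ of 65 are assumptions. The change should be made, but the trial's validity does not depend on it.

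**What to change.** - In SAP 4.8.1 and 4.1, delete the significance trigger. Always run an ANCOVA of change in ISQ on treatment and day-1 ISQ, with centre as a fixed effect, and report it beside the unadjusted permutation test, which stays primary.
- Use the same covariates in the multiple-imputation analysis instead of leaving adjustment to be decided by need.
- State the assumption that the coating does not affect ISQ at placement. If it did, the change analysis and the adjusted analysis would estimate different quantities.
- Record the change in SAP section 6 before treatment groups are revealed.

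The cost is SAP wording and one more result to report, with no new data or subjects. If allocation was not blocked within centre and centre explains no variance, the centre terms cost the adjusted analysis up to about 2 points of power; Protocol 18.9 does not settle how blocks relate to centres. How lost implants are scored is a separate matter and is left as it is.
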